8.4.2 Calculation or derivation of safety variable(s)

The following safety data will be collected: vital signs, physical examination, hematology, clinical chemistry, urinalysis, and reported AEs.

Change from baseline (Week 0) to each post-treatment time point where scheduled assessments were made will be calculated for relevant measurements. Adverse events will be summarized by means of descriptive statistics and qualitative summaries.

8.4.3 Calculation or derivation of patient reported outcome variables

8.4.3.1 Asthma Control Questionnaire (ACQ-6)

The outcome variable for ACQ-6 will be the change in mean score from baseline (Week 0) to EOT (Week 12).

Asthma control responder status will be categorized according to the following limits (Juniper et al 2005):

- ACQ-6 (EOT) \leq 0.75 \rightarrow Well controlled
- $0.75 < ACQ-6 (EOT) < 1.5 \rightarrow Partly controlled$
- ACQ-6 (EOT) \geq 1.5 \rightarrow Not well controlled

8.4.4 Calculation or derivation of pharmacokinetic variables

Due to the limited sampling schedule, the PK assessment will be primarily based on the observed steady-state serum trough (pre-dose) concentrations, C_{trough}. Empirical evaluation of potential impact of demographic covariates and ADA on C_{trough} will be conducted. The PK data and parameters from this study will be reported in the CSR.

8.4.5 Calculation or derivation of benralizumab immunogenicity variables

ADA assessments will be conducted utilizing a tiered approach (screen, confirm, titer).

8.5 Methods for statistical analyses

The analysis of the efficacy endpoints will include all data captured during the 16-week treatment period, including follow-up (where applicable), unless the patient or their parent/legal guardian withdraws consent/assent to study participation, regardless of whether study treatment was prematurely discontinued, or delayed, and/or irrespective of protocol adherence.

Demography and baseline characteristics will be summarized by treatment group for the full analysis set.

8.5.1 Analysis methods for antibody endpoints

Geometric mean fold rises for the HAI and MN antibody measurements are defined as:

 $GMFR=antilog_z$ (mean $[log_z x]$)

Where x is the post-dose HAI or MN antibody titer fold rise from Week 8 and z is the natural logarithm.

Geometric mean titers for the HAI and MN antibody measurements are defined as:

GMT=antilog_z (mean [log_z y])

Where y is the HAI or MN antibody titer and z is the natural logarithm.

The analysis of the antibody endpoints—strain-specific GMFRs and GMTs—will be performed on the vaccine immunogenicity analysis set. GMFRs and GMTs will be summarized by treatment group. For GMFR and GMT, the geometric least square mean ratio between treatment groups (placebo/benralizumab) will be calculated via an ANCOVA model on the log-transformed variable, adjusting for treatment group. The least square geometric mean ratio will be provided with associated 90% CI.

Antibody response is defined as a \geq 4-fold rise in HAI or MN antibody from Week 8. The proportion of patients who experience a post-dose antibody response at Week 12 and corresponding 90% Clopper-Pearson exact CI will be summarized by treatment group.

The proportion of subjects who achieve a post-dose HAI antibody titer ≥40 at Week 12 and corresponding 90% Clopper-Pearson exact CI will be summarised by treatment group.

The proportion of patients who achieve a post-dose HAI antibody titer ≥320 at Week 12 and corresponding 90% Clopper-Pearson exact CI will be summarized by treatment group.

No interim blinded review is planned.

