The analysis of the anti-influenza antibody response endpoints—strain-specific GMFRs and GMTs—will be performed on the immunogenicity analysis set, defined as all randomized patients who received at least 1 dose of planned investigational product (ie, 1 dose of influenza vaccine plus 1 dose of benralizumab or placebo), had pre- and post-dose HAI antibody measurements, had pre- and post-dose MN antibody measurements, and had no protocol deviation judged to have the potential to interfere with the generation or interpretation of an humoral response to the influenza vaccine. GMFRs and GMTs will be summarized by treatment group, and the group ratio of GMFRs (influenza vaccine divided by benralizumab and influenza vaccine) and GMTs and their corresponding 90% confidence intervals (CIs) will be constructed.

The antibody response to the influenza vaccine is defined as a ≥4-fold rise in HAI from Week 8. The proportion of patients who experience a post-dose HAI antibody response at Week 12 and corresponding 90% Clopper-Pearson exact CI will be summarized by treatment group.

The proportion of patients who achieve a post-dose HAI antibody titer ≥40 at Week 12 and corresponding 90% Clopper-Pearson exact CI will be summarized by treatment group.

The proportion of patients who achieve a post-dose HAI antibody titer ≥320 at Week 12 and corresponding 90% Clopper-Pearson exact CI will be summarized by treatment group.

The antibody response to the influenza vaccine is also defined as a ≥4-fold rise in MN antibody from Week 8. The proportion of patients who experience a post-dose MN antibody response at Week 12 and corresponding 90% Clopper-Pearson exact CI will be summarized by treatment group.

For GMFR and GMT, the geometric least square mean ratio between treatment groups (placebo/benralizumab) will be calculated via an analysis of covariance (ANCOVA) model on the log-transformed variable, adjusting for treatment group. The least square geometric mean ratio will be provided with associated 90% CI.

No interim blinded review is planned.

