2. STUDY OBJECTIVES

2.1 Primary Objective

Objective	Endpoint
To evaluate the potential effect of benralizumab on the humoral immune response following seasonal influenza virus vaccination in adolescent and young adult patients with severe asthma	Post-dose strain-specific hemagglutination-inhibition (HAI) antibody geometric mean fold rises (GMFRs) from Week 8
	Post-dose strain-specific serum HAI antibody geometric meant titers (GMTs) obtained at Week 12
	• Proportion of patients who experience a strain-specific post-dose antibody response at Week 12 with antibody response defined as a ≥4-fold rise in HAI antibody titer from Week 8
	• Proportion of patients who achieve a strain-specific post-dose HAI antibody titer ≥40 at Week 12

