8.2 Sample size estimate

The study will have an estimated sample size of 50 patients in each treatment group. No formal statistical hypotheses will be tested. The sample size justification is based on the precision of the estimate of the GMTs (as $GMT_{vaccine} / GMT_{benralizumab+vaccine}$). With 50 patients per arm, the 90% CI for the GMT ratio would be 0.67 to 1.48, assuming an observed ratio of 1, and that the log (post-dose HAI antibody titer or post-dose MN antibody titer) is normally distributed with a standard deviation (SD) of 1.2 on the natural log scale (Langley et al 2013). No formal statistical hypotheses will be tested.

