8.3.3 Vaccine immunogenicity analysis set

The vaccine immunogenicity analysis set will include all randomized subjects who received at least 1 dose of planned IP (ie, 1 dose of influenza vaccine, and plus 1 dose of benralizumab or placebo), had pre- and post-dose HAI and MN antibody measurements, and had no protocol deviation judged to have the potential to interfere with the generation or interpretation of an antibody response. The analyses conducted using this analysis set will be based on the actual treatment received. Protocol deviations will be reviewed by the study team before unblinding.

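### The GMFR and GMT ratios are modelled on treatment group alone, so the Week 8 titer available for every analysed patient is not used to sharpen or cross-check them

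*Protocol*

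**What the plan says.** Strain-specific HAI GMFR is a primary endpoint (Protocol Section 2.1: "Post-dose strain-specific hemagglutination-inhibition (HAI) antibody geometric mean fold rises (GMFRs) from Week 8"), listed next to the Week 12 HAI GMT. Section 8.5.1 defines the GMFR by "Where x is the post-dose HAI or MN antibody titer fold rise from Week 8". The placebo/benralizumab ratio for GMFR and for GMT "will be calculated via an ANCOVA model on the log-transformed variable, adjusting for treatment group", and the statistical methods part of the synopsis repeats this: "calculated via an analysis of covariance (ANCOVA) model on the log-transformed variable, adjusting for treatment group". No covariate is named in either place. The output is an interval: "The least square geometric mean ratio will be provided with associated 90% CI".

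The Week 8 sample is drawn before the vaccine is given (Table 2 footnote; Section 4.2). Patients enter the vaccine immunogenicity analysis set only if they "had pre- and post-dose HAI and MN antibody measurements" (Section 8.3.3). No hypothesis is tested. Section 8.2 rests the sample size on precision alone: "With 50 patients per arm, the 90% CI for the GMT ratio would be 0.67 to 1.48, assuming an observed ratio of 1", where the log post-dose titer "is normally distributed with a standard deviation (SD) of 1.2 on the natural log scale".

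**The concern.** With treatment as its only term, the stated ANCOVA is a two-sample comparison. For GMFR the response is log Week 12 titer minus log Week 8 titer, which imposes a slope of 1 on the Week 8 value. For GMT the slope is 0. Neither slope is estimated, although the data to estimate it exist for everyone analysed.

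Two things follow. First, precision is the trial's only stated design criterion, and some of it may be left unused. Second, randomization is stratified by age group only (Section 6.5), and prior influenza vaccination is excluded only within 90 days of randomization (Section 3.2), so Week 8 titers can differ between arms by chance. For a true slope between 0 and 1, such a difference moves the GMFR ratio one way and the GMT ratio the other, and two primary endpoints could disagree for no biological reason.

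**Working it through.** **Inputs from the protocol.** 50 per arm, SD 1.2 for log Week 12 titer, two-sided 90% CI (Sections 8.2 and 8.5.1).

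**Assumptions.** The protocol gives neither the Week 8/Week 12 correlation r nor the Week 8 SD. I take r = 0.3, 0.5 and 0.7 with a Week 8 SD of 1.2, then vary that SD.

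**Step 1: the plan's own figure.** SE of the log GMT ratio = 1.2 × √(2/50) = 0.24. The CI at an observed ratio of 1 is exp(±1.645 × 0.24) = 0.674 to 1.484. This matches the stated 0.67 to 1.48.

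**Step 2: variances.** Let s0 and s1 be the Week 8 and Week 12 SDs.
- Log fold rise: s1² + s0² − 2·r·s0·s1
- Week 8-adjusted: s1²·(1 − r²)
- Difference: (s0 − r·s1)². This is never negative, and is zero only when the true slope r·s1/s0 equals 1.

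With equal SDs the ratio of the first variance to the second is 2/(1 + r).

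**Step 3: 90% CIs for the GMFR ratio at an observed ratio of 1, both SDs 1.2.**

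| r | SD of log fold rise | adjusted SD | CI, fold rise | CI, adjusted | variance ratio |
|---|---|---|---|---|---|
| 0.3 | 1.420 | 1.145 | 0.63–1.60 | 0.69–1.46 | 1.54 |
| 0.5 | 1.200 | 1.039 | 0.67–1.48 | 0.71–1.41 | 1.33 |
| 0.7 | 0.930 | 0.857 | 0.74–1.36 | 0.75–1.33 | 1.18 |

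At r = 0.5 the unadjusted analysis would need 50 × 1.33 ≈ 67 per arm to match the adjusted one. A simulation of 5,000 trials per setting gave variance ratios of 1.53, 1.33 and 1.16. The extra degree of freedom costs about 1% at 100 patients.

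The adjusted intervals also compare with the unadjusted GMT interval, which stays at 0.67–1.48 whatever r is.

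**Step 4: sensitivity to the Week 8 SD.** For r from 0.3 to 0.8 the variance ratio for GMFR runs from about 1.00 to 1.22 with a Week 8 SD of 0.9, and from 1.56 to 1.99 with an SD of 1.5. At SD 0.9 and r = 0.7 the slope is 0.7 × 1.2/0.9 = 0.93 and the ratio is 1.005, so the gain over GMFR is negligible.

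**Step 5: chance imbalance.** A Week 8 log difference d moves the log GMFR ratio by −(1 − slope)·d and the log GMT ratio by slope·d. Take one standard error, d = 0.24 (Week 8 GMT ratio exp(0.24) = 1.27), with no drug effect and equal SDs:
- r = 0.3: GMFR ratio 0.85, GMT ratio 1.07
- r = 0.5: GMFR ratio 0.89, GMT ratio 1.13
- r = 0.7: GMFR ratio 0.93, GMT ratio 1.18

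In simulation the fold-rise estimate depended on the imbalance with slopes of −0.70, −0.50 and −0.29. After adjustment the dependence was about 0.

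**Step 6: the two adjusted models coincide.** With log Week 8 titer as covariate, modelling log fold rise or log Week 12 titer gives the same treatment ratio (simulated difference below 1e-14).

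**The case against.** The strongest objection is that Week 8 is not a randomization baseline. It follows doses at Weeks 0 and 4, and Table 2 schedules no earlier influenza titer. The unadjusted GMFR and GMT contrasts are plain randomized comparisons, valid even if benralizumab moves the Week 8 titer. Regression on Week 8 conditions on something treatment may have changed, in a trial that asks whether the drug alters humoral immunity.

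A reader might infer that adjustment removes any drug-induced Week 8 shift. It does so only under one definition of no effect. Suppose benralizumab lowers the Week 8 log titer by 0.2, with r = 0.3, 0.5 and 0.7:
- If the shift carries to Week 12 at slope r, the adjusted ratio is 1.00.
- If both titers fall by 0.2, GMFR reads 1.00 and the adjusted ratio exp(0.2(1 − r)) = 1.15, 1.11, 1.06.
- If only Week 8 falls, GMT reads 1.00 and the adjusted ratio exp(−0.2r) = 0.94, 0.90, 0.87.

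This stands, and it rules out substituting the adjusted ratio for the GMFR ratio. So does the result of Step 6: substitution would merge two endpoints that the protocol lists separately, and the reported ratio would no longer be the quotient of the per-arm GMFRs.

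It is also fair to say that Section 8.2 claims precision only for the GMT ratio, that no test or margin depends on any of this, and that a SAP could add a covariate. The last point carries less weight, because the protocol itself names the model and its only term, in two places. None of this argues against reporting an adjusted ratio as well.

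**Conclusion.** The point holds as a cheap improvement to the analysis. The named model leaves the Week 8 titer unused as a covariate. Apart from one degree of freedom, the unadjusted GMFR comparison is never more precise than the adjusted one. Under the stated assumptions its log-scale CI is wider by a factor of √1.54, √1.33 or √1.18 at r = 0.3, 0.5 or 0.7. The size rests on a correlation and a Week 8 SD that the protocol does not give, and for GMFR it shrinks to almost nothing when the true slope is near 1.

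Two stronger readings are not supported. A reader might infer that the GMFR ratio is biased or carries a Week 8 imbalance in full. It carries the fraction (1 − slope) with reversed sign, while the GMT ratio carries the slope fraction in the same direction. Under chance imbalance alone, both are unbiased on average over randomizations. A reader might also infer that a stated figure or an error rate is wrong. The 0.67 to 1.48 interval reproduces, and no hypothesis is tested.

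**What to change.** In Section 8.5.1 and the synopsis, prespecify for each strain and assay an ANCOVA of log Week 12 titer (equivalently log fold rise) on treatment plus the log Week 8 titer of the same strain and assay. Report its placebo/benralizumab ratio with 90% CI, labelled as vaccine response given pre-vaccination titer. Keep the unadjusted GMFR and GMT ratios as now specified, and show the Week 8 GMTs by arm so that any disagreement between the ratios can be read against them.

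The cost is a sentence or two of text and one degree of freedom, with no new data. There are two downsides to state. The model assumes a common linear slope. The adjusted ratio equals the total effect on Week 12 titer only if treatment has not moved the Week 8 titer, which is why the unadjusted ratios must stay.

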1.2 Rationale for study design, doses and control groups

This study is designed to investigate the potential effect of benralizumab on the antibody response to the seasonal influenza virus vaccine in patients 12-21 years of age with asthma. Benralizumab (30 mg) will be given subcutaneously (SC) at Weeks 0, 4, and 8 weeks, at which time benralizumab levels will reach steady state. Patients will then receive 1 dose of intramuscular (IM) seasonal influenza virus vaccine at Week 8 and samples drawn at Week 8 and Week 12 to measure the antibody response to the influenza virus

The immune response, as assessed by evaluation of antibody responses to the influenza vaccine in the group receiving benralizumab versus placebo will be assessed by

- Post-dose strain-specific HAI antibody geometric mean folder rises (GMFRs) from Week 8
- Post-dose strain-specific HAI antibody geometric mean titers (GMTs) obtained at Week 12
- Proportion of patients who experience a strain-specific post-dose antibody response at Week 12 with antibody response defined as a ≥4-fold rise in HAI antibody titer from Week 8
- Proportion of patients who achieve a strain-specific post-dose HAI antibody titer ≥40 at Week 12
- Proportion of patients who achieve a strain-specific post-dose HAI antibody titer ≥320 at Week 12
- Post-dose strain-specific MN antibody GMFRs from Week 8
- Post-dose strain-specific serum MN antibody GMTs obtained at Week 12
- Proportion of patients who experience a strain-specific post-dose antibody response at Week 12 with antibody response defined as a ≥4-fold rise in MN antibody titer from Week 8

The benralizumab dose (30 mg SC, fixed) is based on all available safety and efficacy data, as well as population exposure-response modeling and stochastic trial simulations from earlier phase benralizumab trials. Other stable asthma therapies on top of inhaled corticosteroids/long-acting β_2 agonists (ICS/LABA) that are within expert guidance and not restricted per protocol are allowed in order to accommodate local standards of care.

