6.5 Methods for assigning treatment groups

Randomization codes will be assigned strictly sequentially in each stratum (adolescents [12-17 years of age] and young adults [18-21 years of age]) as patients become eligible for randomization.

Patients who fail to meet the inclusion/exclusion criteria should not, under any circumstances, be enrolled or receive study medication. There can be no exceptions to this rule.

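### The ANCOVA for the GMT and GMFR ratios names only treatment group and leaves out the age stratum used in randomization, so its valid 90% intervals are slightly wider than needed if age predicts titer

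*Protocol*

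**What the plan says.** Section 8.5.1 gives the ratio of geometric least-squares means, placebo over benralizumab, with a 90% CI. It states that this ratio "will be calculated via an ANCOVA model on the log-transformed variable, adjusting for treatment group". The synopsis (Statistical methods) has the same model: "analysis of covariance (ANCOVA) model on the log-transformed variable, adjusting for treatment group". Neither place names a covariate or a stratification factor.

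Section 6.5 describes the allocation: "Randomization codes will be assigned strictly sequentially in each stratum (adolescents [12-17 years of age] and young adults [18-21 years of age"]). Section 3.3 sets the ratio at 1:1, and section 1.4 requires at least half of the patients to be adolescents.

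Section 8.2 tests no hypothesis and sets no margin. Instead, "The sample size justification is based on the precision of the estimate of the GMTs": with 50 per arm and an observed ratio of 1, the 90% CI is given as 0.67 to 1.48, on the assumption that the log titer "is normally distributed with a standard deviation (SD) of 1.2 on the natural log scale".

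For the fold rise, section 8.5.1 takes Week 8 as the reference: "Where x is the post-dose HAI or MN antibody titer fold rise from Week 8".

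**The concern.** Treatment is the comparison of interest, not a covariate, so an ANCOVA with treatment as its only term has nothing to adjust for. The design treats age as important enough to stratify on, but the analysis then ignores it.

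Stratified 1:1 allocation balances the arms on age. If age predicts titer, the true variance of the treatment difference falls. A treatment-only model leaves the age variance in its residual, so its standard error does not show the benefit. The interval then covers a little more than 90% and is wider than it need be.

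Only precision is at stake. That still deserves a line, because precision of the GMT ratio is the sole basis on which section 8.2 justifies 100 patients.

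Omitting the Week 8 titer from the GMT model is not criticized. Week 8 follows the Week 0 and Week 4 doses, and section 1.2 describes the dosing as bringing drug levels to the point "at which time benralizumab levels will reach steady state". Adjusting for a titer measured on treatment would change what the ratio means, and the GMFR already uses Week 8 as its reference.

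**Working it through.** **Inputs from the protocol.** 50 patients per arm and log SD 1.2 (section 8.2); two-sided 90% CI; 1:1 allocation (3.3); two age strata (6.5); adolescent share p of at least 0.5 (1.4).

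**Assumed, because the protocol does not give them.** p from 0.5 to 0.7; the fold difference F in GMT, or in fold rise, between the age strata; and, for the GMFR, the Week 8 log SD s8 (0.8 to 1.5) and its correlation rho with the Week 12 log titer (0.3 to 0.7). Total log SD is held at 1.2.

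**1. The plan's own figure.** Standard error = 1.2 × √(2/50) = 0.24. With z = 1.645 the half-width is 0.3948, giving exp(±0.3948) = 0.674 to 1.484, which matches 0.67 to 1.48. With t on 98 df (1.6606) the half-width is 0.3985, giving 0.671 to 1.490. The stated interval therefore belongs to the treatment-only model.

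**2. GMT ratio with the age stratum added.** The share of log-titer variance explained by the stratum is R² = p(1−p)(ln F)²/1.44, and the log-scale interval narrows by 1 − √(1−R²). The lost degree of freedom costs about 0.01 percentage points of width. The equivalent number per arm is 50/(1−R²).

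| F | R², p = 0.5 to 0.7 | Narrowing | 90% CI at ratio 1 | Equivalent n per arm |
|---|---|---|---|---|
| 1 (no difference) | 0 | none | 0.671-1.490 | 50 |
| 1.25 | 0.0086-0.0073 | 0.4% | about 0.672-1.487 | 50.4 |
| 1.5 | 0.0285-0.0240 | 1.4-1.2% | about 0.675-1.482 | 51.5-51.2 |
| 2 | 0.0834-0.0701 | 4.3-3.6% | 0.683-1.465 to 0.681-1.469 | 54.6-53.8 |

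**3. GMFR ratio with the age stratum added.** The same formula applies, with 1.44 replaced by the variance of the log fold rise, 1.44 + s8² − 2·rho·1.2·s8 (SD 0.86 to 1.62 over the assumed grid). The narrowing is 0.7-2.8% if the strata's fold rises differ 1.5-fold and 2.0-8.5% if they differ 2-fold.

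**4. Coverage of the treatment-only interval.** With balance within strata it is 2Φ(1.645/√(1−R²)) − 1. At p = 0.5 this gives 90.5% for a 1.5-fold GMT difference and 91.4% for 2-fold. Simulation (20,000 trials per scenario, p = 0.5 to 0.7) gave 90.4-90.8% and 90.8-91.6% respectively, against 89.5-90.4% with the stratum in the model. When treatment was allocated without regard to stratum (R² = 10%), treatment-only coverage was about 90%: still valid, but no longer conservative.

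**5. Size of a supportive Week 8 adjustment (see the fix).** The adjusted log SD is 1.2√(1−rho²), giving half-widths of 0.380, 0.345 and 0.285 at rho 0.3, 0.5 and 0.7. Compared with the narrower of the two planned treatment-only intervals, the gain runs from 0.1% (s8 0.8, rho 0.7) to 20.8% (s8 1.5, rho 0.7). This range does not measure the omission of the stratum.

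**The case against.** The strongest objection is that nothing here is wrong. The interval is valid, the planned precision was worked out for the treatment-only model, and that model delivers it at 50 per arm. No hypothesis is tested, so no decision can be altered. The strata are adjacent age bands, and nothing in the protocol says they respond differently. At a 1.5-fold difference the gain is worth little more than one patient per arm. All of this stands, and it is why the point is minor.

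A second objection is that covariates belong in the SAP, which is not shown, and that speaking of ANCOVA and least-squares means hints at covariates still to be listed. This carries less weight. The protocol does not defer the model; it writes it out in two places with one term. If the SAP adds the stratum, the protocol's sentence should be brought into line with it.

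Third, the conservatism requires balance within strata as well as a prognostic age effect, and section 6.5 gives no block size. That condition is real. Balance is a fair reading of 1:1 allocation within strata, and without it the planned interval is still valid.

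Finally, a Week 8-adjusted ratio goes beyond the omission itself. That is accepted: it is optional, and the case for the stratum does not rest on it.

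**Conclusion.** The point holds as a minor one. The protocol names a model with treatment as its only term in a trial randomized within age strata. The resulting 90% intervals are valid and free of bias. If age is prognostic and the arms are balanced within strata, they are slightly conservative: for the GMT ratio 0 to about 4% wider on the log scale than they need be for stratum differences up to 2-fold, and for the GMFR ratio up to about 8.5% under the most favourable assumed correlation and SD.

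These sizes rest on assumed age effects, adolescent shares of 50-70%, and, for the GMFR, an assumed Week 8 SD and correlation. If age does not matter, the gain is nil and the cost of adding the stratum is negligible.

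**What to change.** In section 8.5.1 and in the synopsis, state for each strain and assay:

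1. GMT: log(Week 12 titer) = treatment + age stratum (12-17, 18-21).
2. GMFR: log(Week 12 titer / Week 8 titer) = treatment + age stratum.

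Keep both as the planned placebo/benralizumab ratios with 90% CIs. Each equals the ratio of the summarized group values whenever the arms have the same share of adolescents.

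Optionally, report one supportive ratio with log(Week 8 titer) added. If so, say that it is the same whether GMT or GMFR is the outcome, so it counts as one result. Say also that, because Week 8 follows two doses, it excludes any drug effect on pre-vaccination titers and so replaces neither planned ratio.

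The cost is one or two sentences. The age stratum is known at randomization, and section 8.3.3 already requires a pre-vaccination titer for the analysis set, so no new data or visits are needed.

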8. EVALUATION AND CALCULATION OF VARIABLES

8.1 Statistical considerations

- All personnel involved with the analysis of the study will remain blinded until database lock
- Analyses will be performed by AstraZeneca or its representatives
- The SAP will be prepared prior to first patient randomized and any subsequent amendments will be documented, with final amendments completed prior to unblinding of the data

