8.3 Definitions of analysis sets

Antibody endpoints to the influenza vaccine—strain-specific HAI and MN antibody GMFRs and GMTs—will be analyzed using the vaccine immunogenicity analysis set. All remaining efficacy analyses will be performed using an Intent-to-Treat (ITT) approach based on the full analysis set. For consistency, demographic and baseline characteristics will be presented using the full analysis set. Safety objectives and ADA will be analyzed based on the Safety analysis set.

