8.3.2 Full analysis set

All patients randomized and receiving any IP will be included in the full analysis set, irrespective of their protocol adherence and continued participation in the study. Patients will be analyzed according to their randomized treatment, irrespective of whether or not they have prematurely discontinued, according to the ITT principle. Patients who withdraw consent to participate in the study will be included up to the date of their study termination.

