8.4.1.1 Humoral immune response following seasonal influenza virus vaccination

The benralizumab versus placebo humoral immune responses following seasonal influenza virus vaccination will be assessed by

Primary objective:

- Post-dose strain-specific HAI antibody geometric mean folder rises (GMFRs) from Week 8
- Post-dose strain-specific HAI antibody geometric mean titers (GMTs) obtained at Week 12
- Proportion of patients who experience a strain-specific post-dose antibody response at Week 12 with antibody response defined as a ≥4-fold rise in HAI antibody titer from Week 8
- Proportion of patients who achieve a strain-specific post-dose HAI antibody titer ≥40 at Week 12

Secondary objectives:

- Proportion of patients who achieve a strain-specific post-dose HAI antibody titer ≥320 at Week 12
- Post-dose strain-specific microneutralization (MN) antibody GMFRs from Week 8
- Post-dose strain-specific serum MN antibody GMTs obtained at Week 12
- Proportion of patients who experience a strain-specific post-dose antibody response at Week 12 with antibody response defined as a ≥4-fold rise in MN antibody titer from Week 8

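### Two of the four primary endpoints, and two secondary proportions, have no specified between-arm estimate

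*Protocol*

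**What the plan says.** The primary objective in Section 2.1 is "To evaluate the potential effect of benralizumab on the humoral immune response following seasonal influenza virus vaccination". Section 8.4.1.1 introduces its list of endpoints with "The benralizumab versus placebo humoral immune responses following seasonal influenza virus vaccination will be assessed by". Eight follow:

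- **Primary:** HAI GMFR, HAI GMT, HAI ≥4-fold rise, HAI titer ≥40.
- **Secondary:** HAI titer ≥320, MN GMFR, MN GMT, MN ≥4-fold rise.

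Section 8.5.1 and the synopsis (Statistical methods) then give the methods. For GMFR and GMT, a placebo/benralizumab ratio of geometric least-squares means comes from a model on the log scale: "The least square geometric mean ratio will be provided with associated 90% CI". For the ≥4-fold responses, the proportion "at Week 12 and corresponding 90% Clopper-Pearson exact CI will be summarized by treatment group". The HAI ≥40 and ≥320 endpoints are treated the same way; for ≥40, the synopsis sentence reads in part: "who achieve a post-dose HAI antibody titer ≥40 at Week 12 and corresponding 90% Clopper-Pearson exact CI will be summarized by treatment group".

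On analysis sets, Section 8.3 assigns the vaccine immunogenicity set to the antibody endpoints but spells these out as GMFRs and GMTs. It continues: "All remaining efficacy analyses will be performed using an Intent-to-Treat (ITT) approach based on the full analysis set". Section 8.3.2 defines that set: "All patients randomized and receiving any IP will be included in the full analysis set".

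**The concern.** The objective is an effect of benralizumab, and in a randomized placebo-controlled trial an effect is a contrast between arms. The protocol supplies one for the continuous endpoints and, in the same section, omits it for the binary ones, although all eight carry the same stated purpose. In a study with no formal hypothesis test, the estimate and its interval are the whole result, so an endpoint without a between-arm estimate does not deliver its part of the objective.

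Readers will compare two per-arm intervals by eye, and overlap is a poor guide to the difference. In a trial asking whether a drug impairs vaccine response, taking overlap as reassurance errs in the unsafe direction.

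The denominator is a secondary matter. Read literally, Section 8.3 sends the proportions to the full analysis set, which can include patients with no Week 12 titer.

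**Working it through.** **The plan's own precision figure.** Section 8.2 gives 50 per arm, SD 1.2 on the natural log scale and an observed ratio of 1. The 90% CI is exp(±1.645 × 1.2 × √(2/50)) = exp(±0.395) = 0.67 to 1.48, as stated. It concerns the GMT ratio only; no precision statement exists for any proportion.

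**What is fixed for each endpoint (synopsis and Section 8.5.1).**

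| Endpoint | Level | Per-arm summary | Between-arm estimate |
|---|---|---|---|
| HAI GMFR, HAI GMT | primary | yes | ratio, 90% CI |
| HAI ≥4-fold, HAI ≥40 | primary | proportion, 90% CI | none |
| MN GMFR, MN GMT | secondary | yes | ratio, 90% CI |
| HAI ≥320, MN ≥4-fold | secondary | proportion, 90% CI | none |

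**Size of the missing interval.** The protocol states no response rates, so all rates below are assumptions. The 90% Miettinen-Nurminen limits for a difference d are the values of δ that solve

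|d − δ| / √{[p̃₁(1−p̃₁)/n₁ + p̃₂(1−p̃₂)/n₂] × N/(N−1)} = 1.645,

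where p̃₁ and p̃₂ are the maximum-likelihood proportions under p₁ − p₂ = δ and N = n₁ + n₂. With equal counts in the two arms:

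| Evaluable per arm | Responders per arm | Half-width (points) |
|---|---|---|
| 50 | 30 (60%) | 16.0 |
| 50 | 35 (70%) | 15.1 |
| 50 | 40 (80%) | 13.4 |
| 50 | 45 (90%) | 10.6 |
| 50 | 48 (96%) | 8.0 |
| 45 (assumed) | 27 (60%) | 16.9 |
| 45 (assumed) | 31 (69%) | 16.1 |
| 45 (assumed) | 36 (80%) | 14.2 |

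The choice of method matters little here: at 50 per arm and 80%, Newcombe and Wald both give 13.2.

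**What per-arm intervals show and hide.** Clopper-Pearson 90% limits are the 0.05 quantile of Beta(x, n−x+1) and the 0.95 quantile of Beta(x+1, n−x).

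- 30/50 on benralizumab and 35/50 on placebo: per-arm intervals 47.4-71.7% and 57.6-80.5%. The difference is -10.0 points, 90% CI -25.3 to +5.8.
- 32/50 on benralizumab and 40/50 on placebo: per-arm intervals 51.4-75.3% and 68.4-88.7%, which overlap. The difference is -16.0 points, 90% CI -30.3 to -1.2, which excludes zero.
- Against 40/50, the per-arm intervals first separate when the other arm falls to 28/50 (upper limit 68.0% against lower limit 68.4%), a gap of 24 points.

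**Analysis set.** Sections 8.3 and 8.5.1 and the synopsis each name only GMFRs and GMTs when assigning the immunogenicity set. That set requires vaccination and both pre- and post-dose titers (Section 8.3.3). The full analysis set requires only randomization and any IP. The two can give different denominators for the same primary proportion.

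**The case against.** The strongest reply is that this is SAP territory. Section 8.1 says "The SAP will be prepared prior to first patient randomized", effect measures and interval methods for binary endpoints are commonly set there, and nothing in Section 8.5.1 forbids adding a difference. It may also be said that Section 8.4.1.1 lists variables rather than promising a contrast for each, and that side-by-side proportions suit a study that tests no hypothesis. The HAI proportions are dichotomies of titers that already get a randomized comparison, the trial is sized on the GMT ratio, and a difference can be computed from the reported counts.

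Much of this limits the consequence. It does not remove the point. The protocol does not defer the method for these endpoints: it states one twice, and that method lacks the contrast. The absence of a formal test does not help, because what is missing is an estimate. If the gap is filled later, the effect measure, interval method, direction and denominator are not fixed by the protocol.

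On the analysis set, Section 8.5.2 closes by assigning the non-immunogenicity analyses to the full analysis set, which suggests that the remaining efficacy analyses were meant to be ACQ-6. That is a reasonable reading of intent. The text still names only GMFRs and GMTs for the immunogenicity set, so one clarifying clause is justified.

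**Conclusion.** The point holds. Four of eight antibody endpoints, two of them primary, have a stated method that yields no estimate of the benralizumab-placebo contrast. It should be corrected, but it does not threaten the trial: the primary objective retains ratio estimates through HAI GMT and GMFR, and no decision rule depends on the proportions. With 50 evaluable per arm, the missing 90% interval would be about ±8 to ±16 points for common response rates between 96% and 60%; with 45 per arm it would be about ±14 to ±17 points for rates between 80% and 60%. These widths rest on assumed rates and evaluable numbers. They illustrate the information left out and do not measure a bias. The count of endpoints without a contrast rests on the text alone. The analysis-set ambiguity is a secondary drafting matter.

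**What to change.** In the synopsis and Section 8.5.1, for each strain and each of the four proportions, add the between-arm difference with a 90% CI.

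- **Method:** unstratified Miettinen-Nurminen is one suitable choice and matches the GMFR/GMT model, which adjusts only for treatment group. Stratifying by the randomization age group is optional.
- **Direction:** state it explicitly. The GMT ratio is placebo over benralizumab, so a benralizumab-minus-placebo difference would point the opposite way.
- **Status:** label it as estimation only, in keeping with Section 8.2.
- **Analysis set:** name the set for the proportions in Section 8.3, and make Sections 8.3.2, 8.3.3 and 8.5.1 and the synopsis agree with it.
- **Keep** the per-arm Clopper-Pearson intervals as descriptive.

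The cost is a few sentences and one column per responder table. No extra patients, samples or design change are needed.
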